### 6.2.3 Phase 2b Dose-Ranging Study

The phase 2b study was a randomized, placebo-controlled, double-blind, parallel-group, dose-ranging study to evaluate the efficacy and safety of various doses of nemolizumab in moderate-to-severe AD subjects with severe pruritus (peak pruritus numeric rating scale [PP NRS]  $\geq 7$ ).

A total of 226 adult subjects were randomized (1 subject in the placebo group was randomized but not treated): 57 subjects were randomized to placebo and 169 subjects were randomized to nemolizumab arms (55 subjects to 10 mg, 57 subjects to 30 mg, and 57 subjects to 90 mg). There were 176 subjects (77.9%) who completed the treatment and 44 subjects (19.5%) who discontinued the study. Overall, all demographic and baseline disease characteristics were similar in all treatment groups.

At the Week 24 visit, a greater percent change reduction in Eczema Area and Severity Index (EASI) was observed with the nemolizumab 30-mg dose (least squares mean difference vs placebo = 16.7%) and the difference was statistically significant (95% confidence interval [CI] = -30.2, -3.2;  $p < 0.05$ ) compared to placebo. The nemolizumab 10-mg dose showed marginally significant difference vs placebo (least squares mean difference = 13.6%; 95% CI = -27.3, 0.0;  $p = 0.05$ ). However, the difference between the nemolizumab 90-mg dose and placebo did not achieve statistical significance.

The secondary endpoint of Investigator's Global Assessment (IGA) success (clear/almost clear and 2-point reduction) was not statistically significant at Week 24 (25.5% in nemolizumab 10 mg, 36.8% in 30 mg, 22.8% in 90 mg, and 21.1% in placebo). However, the difference was statistically different for the 30-mg dose compared to placebo at Week 16 (33.3% vs 12.3%;  $p = 0.008$ ). The PP NRS responder (PP NRS improvement  $\geq 4$ ) rate was statistically significant ( $p < 0.05$ ) for the nemolizumab 10-mg and 30-mg doses at Week 24, and all nemolizumab doses were statistically significantly superior to placebo at Week 16 ( $p < 0.05$ ). Nemolizumab demonstrated an early onset of action in pruritus as early as Week 1. In addition, the proportion of EASI-75 responders was statistically significantly greater for nemolizumab 30 mg at Week 24 and for both the 30-mg and 90-mg doses at Week 16 compared to placebo ( $p < 0.05$ ). The sleep disturbance NRS was highly statistically significant for all 3 nemolizumab doses at Week 24 ( $p < 0.001$ ) vs placebo.

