There was 1 non-related AE with a fatal outcome (PPD subject treated with the 10-mg dose died due to non-study drug related aspiration pneumonia and cardiopulmonary arrest). Three suspected unexpected serious adverse reactions (SUSARs) were recorded in the study: exacerbation of AD (10-mg dose, withdrawal from study), septic shock (90-mg dose, sepsis, *Staphylococcus aureus*-positive blood culture, recovered/resolved without sequelae), and phlegmon/cellulitis of the right cheek (30-mg dose, recovered/resolved without sequelae). All doses of nemolizumab were associated with a slightly higher incidence of serious treatment-emergent AEs (TEAEs) (1 [1.8%], 3 [5.5%], 2 [3.5%], and 2 [3.5%] in placebo, 10 mg, 30 mg, and 90 mg, respectively) but not severe TEAEs (6 [10.7%], 3 [5.5%], 5 [8.8%], and 2 [3.5%] in placebo, 10 mg, 30 mg, and 90 mg, respectively) when compared to placebo. There was a comparable percentage of subjects discontinuing treatment due to TEAE in the placebo and active treatment arms. All doses of nemolizumab were associated with a slightly higher incidence of TEAEs when compared to placebo. There was no increase in the incidence of skin infections in the nemolizumab compared to the placebo groups, although there was a higher incidence of non-skin infections with nemolizumab (mainly rhinopharyngitis and upper respiratory tract infections). There was a dose-dependent increase of asthma flares (1 [1.8%], 2 [3.6%], 7 [12.3%], and 10 [17.5%] in placebo, 10 mg, 30 mg, and 90 mg, respectively) in subjects with pre-existing asthma. Events were mostly mild or moderate (1 severe event with highest dose), manageable, and reversible under treatment with study drug. Further, a higher incidence of AD exacerbation in the placebo arm compared to the nemolizumab treatment arms was observed. Local and systemic injection-related reactions (IRRs) occurred more frequently in the placebo compared to the active treatment groups. Finally, there was a low incidence of peripheral edema, with no serious cases and no imbalance with the placebo arm.

The safety and efficacy data generated in the phase 2b dose-finding study supported the selection of the 30-mg dose as the treatment dose for the phase 3 studies.

Based on the safety data from the 3 completed studies, no additional risks for nemolizumab have been identified. Potential important risks to be monitored closely include newly diagnosed asthma or worsening of asthma and infections.

CONFIDENTIAL

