#### 6.3 Risk/Benefit Assessment

Topical medications are the mainstay of AD therapy. Treatment options are however, limited for patients with moderate-to-severe AD whose disease cannot be adequately controlled with topical medications.

Results of previous clinical studies in adults demonstrated that treatment with nemolizumab had a marked effect on AD, pruritus, and pruritus-related sleep loss. Improvements in the symptoms of AD were consistent with the observed improvement in sleep quality (evaluated subjectively) and QoL (evaluated using Dermatology Life Quality Index [DLQI]). Continuous treatment for up to 64 weeks led to improvements in overall AD severity, evaluated with various validated scales commonly used in dermatology clinical trials (ie, EASI, SCORing Atopic Dermatitis [SCORAD], and IGA). Nemolizumab was also well tolerated overall when used as monotherapy or concomitantly with a TCS.

Based on the currently available information on nemolizumab and the risks associated with biologic agents in general, the potential risks of nemolizumab treatment include local or systemic IRRs, newly diagnosed asthma or worsening of asthma, exacerbation of atopic dermatitis, and skin or non-skin infections. The following specific risk-minimization and safety follow-up measures have been planned in this clinical study:

- a. In the phase 2b PPD dose-ranging study, a dose-dependent increase of asthma flares (1 [1.8%], 2 [3.6%], 7 [12.3%], and 10 [17.5%] in placebo, 10-mg, 30-mg, and 90-mg treatment arms, respectively) in subjects with pre-existing asthma was observed. Events were mostly mild or moderate (1 severe event with highest dose), manageable, and reversible under treatment with study drug. The protocol

CONFIDENTIAL

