For the subset of subjects with COVID-19 infection, the following summary tables will be provided additionally and it will be repeated for all TEAEs and Study drug related TEAEs, separately.

- Overall summary of TEAEs
- TEAEs by System Organ Class and Preferred Term
- Serious TEAEs by System Organ Class and Preferred Term
- TEAEs of Special Interest by Category, System Organ Class and Preferred Term

A separate summary below for TEAEs of Special Interest will be provided by periods (initial, maintenance) and repeated for all TEAEs (all causalities) and Study drug related TEAEs.

- Overall Summary of TEAEs of Special Interest
- TEAEs of Special Interest by Category, System Organ Class and Preferred Term
- TEAEs of Special Interest by Category, System Organ Class, Preferred Term and Maximum Severity

Adjudicated events will also be summarized as below by periods (initial, maintenance) and repeated for all TEAEs (all causalities) and Study drug related TEAEs.

This document is confidential.

- Adjudicated TEAEs by System Organ Class and Preferred Term, which are confirmed by Independent Adjudication Committee (IAC).
- Confirmed Adjudicated TEAEs by System Organ Class, Preferred Term and Maximum Severity. Maximum severity will be based on the severity adjudicated by IAC.
- Asthma TEAEs and TEAE of Special Interest reported by Investigator with Adjudication by IAC, which include the data reported by Investigator and adjudications by IAC.

The subgroup summary by country and age group will also be provided for the following summaries. It will be repeated for all TEAEs and Study drug related TEAEs and for Treatment period, Follow-up period and Overall period, separately.

- Overall summary of TEAEs
- TEAEs by System Organ Class and Preferred Term

In addition, the exposure-adjusted incidence rate (i.e., number of subjects per 100 patient-years) will be summarized for all TEAEs (all causalities) and study drug related TEAEs during Treatment Period.

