13.6. Respiratory Assessments

13.6.1. Respiratory Examination and PEF Testing

A respiratory examination consisting of questions regarding medical history of asthma, wheeze, dyspnea, and cough, will be performed for all subjects at Screening, Baseline, Week 4, Week 8, Week 12 and Week 16 of the Initial Period and at Week 20, Week 24, Week 28, Week 32, Week 36, Week 40, Week 44, and Week 48 of the Maintenance Period, as well as at Early termination visit, and at Follow-up.

Respiratory examination questionnaire results will be listed on the Safety population.

PEF testing will be performed for all subjects at Screening, Baseline, Week 4, Week 8, Week 12 and Week 16 of the Initial Period and at Week 20, Week 24, Week 28, Week 32, Week 36, Week 40, Week 44, and Week 48 of the Maintenance Period, as well as at Early termination visit, and at Follow-up.

This document is confidential.

PEF (absolute values and change from Baseline; and change from Week 16 for the Maintenance Period) will be summarized as a continuous variable (scheduled visits only) for the Initial Period and the Maintenance Period. PEF will be summarized separately for the subset of subjects with, and without, a history of asthma.

The number and percentage of subjects with PEF < 80% will be summarized by treatment group, visit (scheduled visits only), and medical history of asthma (with and without history of asthma) for the Initial Treatment Period and the Maintenance Period.

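### SAP 13.1 plans no asthma event rates by asthma history, so worsening of existing asthma and newly diagnosed asthma share one denominator

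*SAP*

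**What the plan says.** **Event tables.** SAP 13.1 defines one asthma category of adverse event of special interest (AESI), covering both new diagnosis and worsening. AESIs, events confirmed by the independent adjudication committee (IAC), and the investigator-versus-IAC comparison are tabulated on the Safety population (index tables 14.3.1.14, .15 and .18 to .22). The exposure-adjusted tables (14.3.1.4.1 and 14.3.1.5.1) use one exposure total per arm. On subgroups, SAP 13.1 states: "The subgroup summary by country and age group will also be provided for the following summaries". The summaries that follow are the overall TEAE table and the SOC/PT table only. SAP 8.6 has no asthma-history subgroup either.

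**Where asthma history is used.** SAP 13.6.1 says "PEF will be summarized separately for the subset of subjects with, and without, a history of asthma", and gives PEF < 80% by history as well. SAP 13.6.2 summarises the Asthma Control Test (ACT), including scores of 19 or less, in subjects with a history of asthma or a de novo diagnosis.

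**Background signal.** Protocol 6.2.3 reports phase 2b asthma flares as "1 [1.8%], 2 [3.6%], 7 [12.3%], and 10 [17.5%] in placebo, 10 mg, 30 mg, and 90 mg, respectively) in subjects with pre-existing asthma". Protocol 6.3 repeats the figures with the same qualifier, "in subjects with pre-existing asthma was observed". The arm sizes are in 6.2.3: "57 subjects were randomized to placebo and 169 subjects were randomized to nemolizumab arms", with "55 subjects to 10 mg, 57 subjects to 30 mg, and 57 subjects to 90 mg"; "1 subject in the placebo group was randomized but not treated".

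**The concern.** The two parts of the asthma risk have different at-risk sets. Only a subject with asthma can worsen, and only a subject without it can be newly diagnosed.

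They are also detected differently. Under the notes to the schedule in Protocol 8.1.2, subjects with a history have PEF and ACT at every visit, while the others have PEF at selected visits only. (SAP 13.6.1 lists PEF at every visit for all subjects, which does not match that schedule or the note in the SAP's own Table 4-3.) Under Protocol 9.2.1.1, PEF < 80% of predicted in a subject with a history is to be reported as an AESI. Without a history, reporting depends on the investigator's judgement of a specialist's report.

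A pooled percentage therefore mixes two risks and two intensities of detection over one denominator. At stake is the absolute risk for patients with asthma, the group in which phase 2b placed the flares and the figure that a benefit-risk statement needs.

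**Working it through.** **1. Reproduce the phase 2b percentages.** Formula: count / arm size.

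| Arm | Calculation | Result | Stated | Denominators that round to it |
|---|---|---|---|---|
| Placebo | 1/56 (1/57) | 1.79% (1.75%) | 1.8% | 55–57 |
| 10 mg | 2/55 | 3.64% | 3.6% | 55–56 |
| 30 mg | 7/57 | 12.28% | 12.3% | 57 only |
| 90 mg | 10/57 | 17.54% | 17.5% | 57 only |

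The divisor is the whole arm. These could be rates among subjects with asthma only if everyone had asthma.

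**2. What the same counts mean among subjects with asthma.** The number with asthma per arm is not given. Protocol 6.1 says only that about 60% of AD patients have some other atopic condition, which is not asthma alone. Assume a share *f*, equal across arms, with all flares in that group. The rate is count / (*f* × arm size), with 56 treated on placebo.

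| Assumed *f* | Placebo | 30 mg | 30 mg minus placebo |
|---|---|---|---|
| whole arm | 1.8% | 12.3% | 10.5 points |
| 0.60 | 3.0% | 20.5% | 17.5 points |
| 0.40 | 4.5% | 30.7% | 26.2 points |
| 0.25 | 7.1% | 49.1% | 42.0 points |

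**3. The same effect in this trial.** 750 subjects at 2:1 gives 500 and 250. Assume *f* = 0.30, so 150 and 75 with asthma; true rates in them of 10% and 2%; and no asthma events in the others.

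- Events: 0.10 × 150 = 15 and 0.02 × 75 = 1.5.
- Pooled rates: 15/500 = 3.0% and 1.5/250 = 0.6%.
- Risk difference: 8 points among subjects with asthma, 2.4 points pooled (0.30 × 8).
- Ratio: 10/2 = 5 and 3.0/0.6 = 5, unchanged.
- Unpooled z: 0.08 / √(0.10×0.90/150 + 0.02×0.98/75) = 2.73; pooled, 0.024 / √(0.03×0.97/500 + 0.006×0.994/250) = 2.65.

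**4. When the ratio does not survive.** Let *r* be the rate with a history and *s* the rate without. The pooled ratio is [*f₁r₁* + (1−*f₁*)*s₁*] / [*f₀r₀* + (1−*f₀*)*s₀*]. With *s* = 0 it equals (*r₁/r₀*) × (*f₁/f₀*), so imbalance in history carries straight through. With *s₁* = *s₀* > 0, new diagnoses pull it towards 1.

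Protocol 8.4.5 stratifies by IGA and PP NRS only. At an assumed 30%, the chance SD of the difference in share is √(0.3×0.7×(1/500+1/250)) = 3.5 points initially. Protocol 8.1 expects about 190 re-randomised, or 190/3 ≈ 63 per arm, which gives √(0.3×0.7×2/63) = 8.2 points in maintenance.

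**The case against.** **The rate can still be obtained.** A reader might infer that the trial will be unable to state the asthma event rate in patients with asthma. The documents do not support that. Medical history is tabulated by treatment group (14.1.3.3.1), and the PEF tables for subjects with a history (14.3.4.4.8 and .9) would show how many there are. AESIs, adjudicated asthma events and medical history are listed by subject (14.3.2.4, 16.2.7.5, 16.2.4.3). SAP Section 2 allows further exploratory analyses. What is missing is a pre-specified table. That stands as a limit on the point, but the split would then be assembled by hand or after unblinding.

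**Asthma history is not ignored.** Protocol 9.2.1.1 gives three referral triggers for subjects with a history. Two of them, PEF < 80% and ACT ≤ 19, already have summaries split by or largely confined to asthma history. This stands too, but both are measurements at visits, not events.

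**The signal is not lost.** Dilution might be read as hiding a signal. In step 3 the ratio is 5 either way and z barely moves. Only absolute rates and risk differences shrink, given balance and no events outside the asthma group.

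**The phase 2b wording is background.** The qualifier can be read as saying where the flares occurred, with counts and arm sizes printed and the same base as neighbouring adverse event figures. No analysis here uses those percentages. Nor do they transfer directly, because Protocol 8.3.3 excludes poorly controlled asthma. Alone, this would not justify a change.

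**No protocol–SAP conflict.** Protocol 10.1.4.5 promises a history split for PEF only, and the SAP delivers it. The IAC and IDMC charters, which hold their own output plans, are not available.

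**Conclusion.** The gap is real and limited. No AESI, IAC-adjudicated or exposure-adjusted table gives asthma event rates by asthma history, although the category joins two risks with different at-risk sets and different reporting rules.

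The effect is on absolute rates and risk differences in subjects with asthma, which pooling scales down to their share of the arm. That share is not in the documents, so the 25–60% range, the 30% share and the 10% versus 2% rates above are all assumptions. It would be wrong to conclude that phase 2b showed a 20–49% flare rate at 30 mg; that range only shows how much depends on the missing denominator. The between-arm ratio holds if history is balanced and events are confined to subjects with asthma. Neither is assured by design, and balance is least secure in the small maintenance arms.

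The change is worth making because the variable is already collected and already used for PEF.

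**What to change.** In SAP 13.1 and its index, add asthma AESI and IAC-confirmed event tables by medical history of asthma:

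- with a history: worsening of asthma;
- without a history: newly diagnosed asthma;
- each with its own number at risk and exposure time, by treatment group and study period.

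Use the history flag already used for PEF, fixed at screening, so that a subject diagnosed during the trial stays in the group without a history. Specify this before unblinding.

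The cost is a few more tables from data already collected, with no change to conduct. Counts in maintenance will be small: about 63 per re-randomised arm, or about 19 with a history at an assumed 30% (0.30 × 63). Those tables should be read as descriptive.

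As a minor clarification, state in Protocol 6.2.3 and 6.3 that 1.8%, 3.6%, 12.3% and 17.5% are percentages of all subjects in each arm and, where available, give the number with pre-existing asthma per arm. This can wait for the next amendment made for other reasons.

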8.2. Key Definitions

Screening Period is a Period of approximately 2-4 weeks before Day 1/Baseline during which subject eligibility is evaluated and standardized background topical therapy is introduced over a run-in Period of at least 2 weeks before Day 1/Baseline.

The Initial Period is defined as Day 1/Baseline to Week 16 (before the Week 16 dose, with last dose at Week 12). If early discontinued during treatment period, it is defined as the period until 4 weeks after last dosing date or early termination date whichever is earlier.

The Maintenance Period is defined as Week 16 (Maintenance Baseline) to Week 48. If early discontinued during treatment period, it is defined as the period until 4 weeks after last dosing date or early termination date whichever is earlier.

Follow-up Period is defined as the post end of treatment period (i.e., 1 day after end of treatment period) to Follow-up visit in respective treatment period.

The Baseline value of the Initial Period will be taken as latest valid value prior to first injection of study drug. For subjects randomized but not treated, the Baseline value will be the latest value prior to the randomization. Week 16 measurements will serve as Baseline measurements for the Maintenance Period (i.e., Maintenance Baseline). If Week 16 measurements are missing for re-randomized subjects, the last valid non-missing measurement in the Initial Period (i.e., before the dosing for Maintenance Period at Week 16 visit) will be taken as the Baseline measurement for the Maintenance Period.

For diary data (e.g., Peak Pruritus (PP) NRS, Sleep disturbance (SD) NRS), the Baseline values will be the weekly prorated average of non-missing subject diary scores reported during the 7 days. A minimum of 4 daily scores out of the 7 days is required to calculate the weekly prorated average score. Refer the details for the analysis visit window for diary data in Section 8.4.

The date of first treatment is defined as the date of first injection of study drug. The date of first treatment is the Baseline date.

The date of last treatment is defined as the date of last injection of study drug.

Study day is defined as the number of days from the date of first treatment and will be calculated as follows:

This document is confidential.

- If the event date \geq date of first treatment, study day = event date – date of first treatment + 1. Study Day 1 is therefore defined as the day of first treatment.

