9.6. Extent of Exposure

The extent of exposure will be summarized for the Initial Period and the Maintenance Period. Summary for Overall Treatment Period (from Initial to Maintenance Period) will be included in the Maintenance Period summary table.

This document is confidential.

The number of subjects exposed will be summarized for the Initial Period and Maintenance Period, and Overall Period (Initial + Maintenance).

- Treatment duration (in days) is calculated as follows, where date of first treatment is defined as the first day of the relevant study Period: [(date of last treatment – date of first treatment) + 1].
- Total number of doses administered will be calculated as the sum of all doses of study drug administered.
- Total number of doses planned will be calculated as the sum of all doses of study drug planned (dispensed) according to the treatment schedule of the treatment group. If a subject missed dosing due to skipped visit or completed a visit without dosing, this missed dose which is supposed to be dispensed will be accounted for the calculation.
- The number of subjects who missed at least one dose
- The number of subjects who missed at least one dose due to COVID-19*
- The number of doses missed
- The number of doses missed due to COVID-19*

**The reason for dose not administered reported in CRF is COVID-19 [This will be identified using Other specify field in CRF].*

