Exposure-adjusted incidence rates of TEAEs is defined as the number of subjects exposed to treatment and experiencing a certain event divided by the total time of all subjects who are at risk for the event. Specially, for subjects with no event the exposure time is the time from the first drug intake to the end of treatment period. Exposure years is calculated as last study drug exposure date minus first study drug exposure date plus one, divided by 365.25 which is the number of days count in a year. This exposure year calculated for each subject is then added cumulatively and is derived for each treatment arm. So each treatment arm will have one value for exposure years (aka. patient years). The exposure year calculation is different in case of subjects who have completed the study or discontinued from the study or having withdrawn from the study due to any reason. Only the event occurred during the treatment period will account for calculation.

Subject listings will be presented for all TEAEs, TEAEs of special interest, serious TEAEs, severe TEAEs, TEAE leading to permanent discontinuation of study drug, TEAEs leading to death and pre-treatment AEs. Subject listings of TEAEs for subjects with COVID-19 infection and adjudicated Asthma TEAEs will also be listed.

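### SAP 13.1 gives two incompatible denominators for the exposure-adjusted adverse event rates, and on the likelier reading of one of them person-time ends nominally 28 days before event counting does

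*SAP*

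**What the plan says.** SAP 13.1 plans exposure-adjusted incidence rates, as subjects per 100 patient-years, for all treatment-emergent events and for study-drug-related ones (Tables 14.3.1.4.1 and 14.3.1.5.1). One paragraph specifies the denominator:

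- The count of subjects with the event is "divided by the total time of all subjects who are at risk for the event".
- It adds that "for subjects with no event the exposure time is the time from the first drug intake to the end of treatment period".
- It then states: "Exposure years is calculated as last study drug exposure date minus first study drug exposure date plus one, divided by 365.25".
- The subject values are added up by arm: "So each treatment arm will have one value for exposure years".
- An exception follows: "The exposure year calculation is different in case of subjects who have completed the study or discontinued from the study or having withdrawn". No rule is given for it.
- On the numerator: "Only the event occurred during the treatment period will account for calculation".

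The last study drug exposure date is not defined. The nearest definition is in SAP 8.2: "The date of last treatment is defined as the date of last injection of study drug". SAP 9.6 uses that date in a formula of the same form for treatment duration: "date of last treatment – date of first treatment) + 1".

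**The concern.** A denominator cannot be specific to each system organ class and preferred term and also be one total per arm. The first two sentences imply that a subject who has the event stops contributing time at onset. The formula that follows has no such cut. Two competent programmers could produce different rates from this paragraph, and both could say they followed it.

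There is a second difference, in where time ends. The second sentence runs time to the end of the treatment period, and events are counted over that whole period. If the formula stops at the last injection, events in the final dosing interval enter the numerator while their time is left out of the denominator. Every rate would then be too high, by a factor that depends on how long the subject was followed.

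These are the only adverse event tables in the SAP index that use person-time. Only Week 16 responders continue, so follow-up is unequal by design, and these two tables are where the SAP allows for that.

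**Working it through.** The documents state no patient-year total or exposure-adjusted rate, so there is no figure to reproduce.

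**Inputs**

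- Target days (SAP 8.4, Table 8-1): Week 12 = Day 85, Week 16 = Day 113, Week 44 = Day 309, Week 48 = Day 337.
- Last scheduled injection (SAP 4.5): Week 12 in the Initial Period, Week 44 in Maintenance. Study drug includes placebo (Protocol 8.4), so Week 44 applies to the Q8W group too.
- Period ends (SAP 8.2): Week 16 and Week 48. After early discontinuation, the end is the earlier of 4 weeks after the last dose and early termination.
- Planned counts: 750 randomized 2:1, so 500 and 250. The Protocol Synopsis expects 190 nemolizumab and 26 placebo subjects in Maintenance, which agrees with its own assumptions: 500 × 0.85 × 0.45 = 191.25 and 250 × 0.85 × 0.12 = 25.5.

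**1. The two definitions side by side**

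| | First two sentences | Formula |
|---|---|---|
| Subject with the event | stops at onset (implied) | not cut |
| Subject without the event | to end of treatment period | to last exposure date |
| Total | differs by event | one per arm |

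The exception does not reconcile them. By the final analysis every subject has completed, discontinued or withdrawn, so it could apply to everyone. It may be meant to invoke the period ends in SAP 8.2, but there is no cross-reference.

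**2. The gap, if last exposure means last injection**

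Initial: 113 − 85 = 28 days. Maintenance: 337 − 309 = 28 days. For early discontinuers 28 days is the cap; a subject with one dose contributes 1 day of time against up to 29 days of event counting.

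For subjects who stay in, 28 days is nominal. Week 12 five days early and Week 16 five days late gives 28 + 10 = 38. A missed Week 12 dose gives 113 − 57 = 56. A Week 16 visit delayed by 8 weeks under Protocol Appendix 2 gives 28 + 56 = 84.

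**3. Periods reported separately, no dropout**

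Inflation = days to period end ÷ days to last injection.

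- Initial: 113/85 = 1.329.
- Maintenance: (337 − 113 + 1)/(309 − 113 + 1) = 225/197 = 1.142.

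The factor is the same in every group, so it cancels from the between-arm ratio.

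**4. Periods combined, planned counts, no dropout**

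- Nemolizumab, pooled: (310 × 113 + 190 × 337)/(310 × 85 + 190 × 309) = 99060/85060 = 1.165.
- Placebo: (224 × 113 + 26 × 337)/(224 × 85 + 26 × 309) = 34074/27074 = 1.259.
- Ratio: 1.165/1.259 = 0.925, so the nemolizumab-to-placebo rate ratio falls by 7.5%.

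Taking the planned 15% dropout from the Week 16 exits, with last doses assumed spread evenly over Days 1, 29, 57 and 85 and a gap of 0 to 28 days for those subjects, gives a fall of 7.1% to 8.1%.

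**5. If exposure runs to the period end**

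The gap in step 2 disappears. Keeping time after a first event still enlarges the denominator. With incidence p and onset uniform over the period, the single-total rate is 1 − p/2 times the at-risk rate: 0.975 at p = 5% and 0.85 at p = 30% (assumed incidences). Between arms at an assumed 5% and 3%, the ratio moves by a factor of 0.975/0.985 = 0.990. At equal incidence it does not move; the shift grows as the incidences diverge.

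**The case against.** The strongest reply is that the SAP says more about these tables than its rate paragraph does. The opening of SAP 13 and Protocol 10.1.4 both present safety summaries by study period for each treatment group, and SAP 6.3 defines as-treated groups period by period. A table title naming the Treatment Period does not imply pooling, because the special-interest and adjudicated event tables carry the same wording in their titles while SAP 13.1 reports them by period. This stands. A reader might infer that the SAP is silent on periods and groups; it is not. Some ambiguity is left, because SAP 13.1 elsewhere describes the treatment period as including both.

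A reader might also infer that the formula makes nemolizumab look safer than placebo by 7.5%, or by about 13% for the groups switched to Q8W or placebo (1.091/1.259 = 0.867). The documents do not support that as the expected result. It needs the last-injection reading and combined periods together. The 7.5% also needs a pooled nemolizumab group that SAP 6.3 does not define for the overall period, and the 13% needs a four-group layout that SAP 13.1 states only for an overall study period that includes follow-up.

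Finally, the SAP could mean the period end by last exposure date. That would remove the 28-day gap but not the conflict between at-risk time and one total per arm.

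**Conclusion.** The contradiction is on the face of SAP 13.1 and needs no assumption. No reading makes the paragraph consistent.

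The end-date mismatch is conditional on last exposure meaning last injection, which SAP 8.2 and 9.6 support but do not settle. On that reading, with by-period reporting and no dropout, rates are about 33% too high in the Initial Period and 14% too high in Maintenance. Absolute rates, and comparisons of one period with the other, would be wrong. The between-arm ratio would be little changed, provided dropout is similar across groups. A ratio shift of about 7.5% belongs only to the less supported combined-period reading.

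If exposure runs to the period end, what remains is a rate lowered by about half the incidence in each arm, with little effect on the ratio when incidences are close. The point is confined to two descriptive tables and is worth correcting before they are produced.

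**What to change.** State one rule for both tables, following the first two sentences of the SAP's own paragraph:

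- For each system organ class and preferred term, subject time runs from the first dose in the period being summarized to the earlier of the first onset of that event in that period and the end of that period as defined in SAP 8.2. Time is summed by the as-treated group of SAP 6.3. Starting at the first dose of the study instead would put Initial Period time into a Maintenance rate.
- Say whether a subject who had the event in the Initial Period is at risk again in Maintenance.
- Delete or reconcile the last-minus-first formula, the single-total sentence and the unspecified exception.
- Confirm that both tables follow the by-period reporting at the start of SAP 13.
- If a rate per total exposure is also wanted, run exposure to the same period end and label it as a separate measure.

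The cost is SAP wording and one derivation for two tables. No new data are needed.
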